
NIH Toolbox measures (from HS to SR), to test if these values are significantly different between older and young participants. Aim 5: (To determine whether the effects of SR on cognitive outcomes are moderated by brain atrophy in younger and older adults. Hypothesis 5a. The effect of mild SR on cognition will be greater among individuals with greater amounts of cortical thinning, smaller hippocampi, and greater WMH volume. This effect will be greater in older relative to younger adults.) Separately for older and young participants, we will perform linear model analyses, with average differences in NIH Toolbox measures (from HS to SR) as outcomes (separately for each outcome). Cortical length, hippocampi size and WMH volume will be used as independent variables. We will apply covariates as independent variables, if they are found to be significant in an initial analysis. Then, we will pool the datasets to include both older and young participants. In the pooled data, we will perform linear model analyses, with average differences in NIH Toolbox measures (from HS to SR) as outcomes. Cortical length, hippocampi size, WMH volume and age group (older vs. younger) will be used as independent variables. We will also use covariates as independent variables, if they are found to be significant in an initial analysis. Aim 6: (To determine whether changes in metabolic or hormonal profiles mediate changes in cognitive function as a result of SR. Hypothesis 6a. The effect of mild SR on cognition will be mediated by changes in hormones (leptin, adiponectin, and insulin).) Separately for older and young participants, and separately for each hormone measure, each outcome (from NIH toolbox) will be analyzed with mediation analysis (Baron and Kenny's method). Sleep type (SR. vs HS) will be the predictor in the analysis. Hormone measure will be used as the potential mediator. As we have multiple measures from each participant, each component analysis in Baron and Kenny's method will be done as linear mixed model analysis, with subject as random effect. Within each mediation analysis, the first analysis will only have one fixed effect: sleep (SR vs. HS). The outcome measure will be the dependent variable. If sleep is found to be significant, then the second analysis will be done with the hormone measure as the dependent variable, and sleep as the fixed effect. If sleep is also found to be significant in the second analysis, then in the final analysis, the outcome measure will be the dependent variable. Fixed effects will be sleep and the hormone measure. If the hormone measure is still found to be significant, and the coefficient of sleep has decreased in absolute value from the first analysis, then a mediation effect of hormone will be concluded.

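### Aim 6 tests a hormone path only after a significant total effect of sleep restriction on cognition and never estimates the indirect effect; this can cost more than half the power when the direct effect is near zero or opposing

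*Combined protocol and SAP*

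**What the plan says.** Hypothesis 6a, under Statistical Procedures, is: "The effect of mild SR on cognition will be mediated by changes in hormones (leptin, adiponectin, and insulin". The method is Baron and Kenny's causal steps, applied to each NIH Toolbox outcome. It is run "Separately for older and young participants, and separately for each hormone measure", and "each component analysis in Baron and Kenny's method will be done as linear mixed model analysis, with subject as random effect". The sequence is:

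1. The cognitive outcome is modelled with sleep (SR, sleep restriction, v HS, habitual sleep) as the only fixed effect. "If sleep is found to be significant, then the second analysis will be done with the hormone measure as the dependent variable".
2. The hormone is modelled on sleep. "If sleep is also found to be significant in the second analysis, then in the final analysis" the outcome is modelled on sleep and the hormone together.
3. "If the hormone measure is still found to be significant, and the coefficient of sleep has decreased in absolute value from the first analysis", mediation is concluded.

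The wording "If sleep is found to be significant" comes with no significance level or sidedness. The section gives no estimate, standard error, interval or test of the indirect effect, and no minimum size for the fall in the coefficient. The sample-size text covers fat mass, weight, intake and energy balance. It gives no effect size or power for cognition, hormones or mediation.

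**The concern.** The hypothesis is about the indirect effect: the SR effect on the hormone (path a) times the hormone's slope on cognition (path b). The total effect on cognition is that product plus the direct effect c′. When c′ is near zero, the total effect is a product of two moderate quantities, and its test is usually weaker than the test of either path. When c′ has the opposite sign, the total effect can vanish although both paths are real. In either case step 1 stops the analysis before the hormone is looked at.

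The final condition has a different weakness. A fall in a coefficient, judged without a size or an interval, says little about how much of the effect the hormone carries.

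What is at stake is how Hypothesis 6a is reported. A stop at step 1 and a hormone path that was examined and found absent would both appear as no mediation, and readers could not tell them apart.

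**Working it through.** **The plan's own power figure.** For paired t-tests with 50 completers the plan gives standardized effects of 0.69/0.36 = 1.92 (fat mass) and 0.91/0.65 = 1.40 (weight gain), with power above 99%. This reproduces: the noncentrality values are 1.92 × √50 = 13.6 and 1.40 × √50 = 9.9, against a critical value near 2.0. It has no bearing on Aim 6, for which no figure is stated.

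**Inputs from the documents.** 50 expected completers among the 66 younger adults (Statistical Procedures); 36 completers to date, both age groups together, and target accrual 79 (Subjects).

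**Assumptions.** Two-sided 0.05 at each step; a = 0.5 SD of the SR−HS difference; hormone-cognition correlation r = 0.5; c′ from −0.1 to +0.3 SD. The documents give no size for the older group, so n = 79 − 66 = 13 is illustrative only.

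**Model.** On paired SR−HS differences, M = a + e₁ and Y = c′ + 0.5M + √0.75·e₂, with e₁ and e₂ standard normal, so both differences have SD 1. The plan's rule needs step 1, path a and path b all significant, and |sleep coefficient| smaller in the final model. The comparator, a two-path test, needs only paths a and b significant.

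**Hand check at n = 36, c′ = 0.** The total effect is 0.5 × 0.5 = 0.25 SD. Its noncentrality is 0.25 × √36 = 1.5, giving power of about 31%. Path a has 0.5 × √36 = 3.0, giving about 83%. Path b is significant in about 89% of simulated trials. The two-path test therefore has about 0.83 × 0.89 = 74%, while the plan's rule cannot exceed the 31% of step 1.

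**Simulation** (40,000 trials per row, Monte Carlo SE at most 0.25 points; loss = 1 − rule/two-path):

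| n | c′ | plan's rule | two-path test | relative loss |
|---|---|---|---|---|
| 36 | −0.1 | 11.9% | 74.0% | 84% |
| 36 | 0 | 25.7% | 73.8% | 65% |
| 36 | +0.1 | 43.0% | 73.9% | 42% |
| 36 | +0.2 | 59.1% | 73.9% | 20% |
| 36 | +0.3 | 68.4% | 73.9% | 7% |
| 50 | 0 | 39.1% | 90.3% | 57% |
| 13 | 0 | 3.0% | 14.7% | 80% |

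**Other paths.** With residual SD 1, n = 50 and a = b = 0.50, power falls from 85.3% to 30.1% at c′ = 0, from 85.4% to 59.8% at c′ = 0.14, from 85.1% to 79.8% at c′ = 0.3, and from 85.0% to 2.1% when c′ exactly cancels the indirect effect. With a = 0.8, b = 0.5 and c′ = 0 it falls from 91.7% to 63.6%, a 31% loss.

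**Mixed-model version.** A small run (250 trials, n = 36, c′ = 0) using random-intercept models gave 23% with the precondition and 47% without.

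**False positives when one path is zero.**
- The coefficient falls by chance in about half of trials.
- The full rule concludes mediation in about 2.5% or less.
- The two-path test errs in about 5% or less.
- A percentile bootstrap of the indirect effect errs in about 5% to 7% at n = 36. At n = 13 it errs in about 7% to 8% when the hormone-cognition slope is zero.

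**The case against.** Hypothesis 6a concerns mediation of an SR effect on cognition, so asking first whether such an effect exists is coherent. The causal-steps rule is named, fully specified and applied to a supplementary aim. Dropping its first step now, with data collection finished and a cognition paper in press, risks a choice made with step-1 results known. Testing every pair without that step also multiplies the tests, while the plan adjusts p-values only where required. All of this stands. It argues for reporting the total effect alongside, and for labelling and multiplicity control; it does not justify withholding the mediation estimate.

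A reader might infer three stronger things, and the documents support none of them.

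- *That the precondition always discards half or more of the power.* The loss depends on paths the plan does not give. Across the assumed values it runs from almost nothing to 98%. The mixed-model run is too small to settle it: if detections under the rule are a subset of the others, 57 of 118 are retained, or 48% (95% interval about 39% to 57%).
- *That any fall in a coefficient counts as proof.* The fall is a fourth condition on top of three significance tests. It removes false positives: with n = 36, a = 0.8, b = 0 and c′ = 0.5, the three tests alone err in about 4% of trials and the full rule in about 2%.
- *That removing the precondition rescues the older group.* At the illustrative n = 13, two-path power is only about 15%, so sample size limits that analysis too.

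The low error rate holds for paired differences. A random-intercept model on raw values mixes between- and within-person association. In one side simulation with no within-person hormone effect (n = 50, assumed ICC 0.7, between-person correlation 0.3, path a and total effect 0.5 to 0.8 SD), the rule concluded mediation in 32% to 36% of trials. That is a separate issue on which this point does not rest, but it favours working with within-person differences.

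**Conclusion.** The point holds in conditional form. Aim 6 does make a significant total effect a precondition, and it never quantifies the effect it is about. The power cost exceeds half when the direct effect is near zero or opposing, under the assumed moderate paths. It is modest once a same-direction direct effect of about 0.3 SD is present. A near-zero direct effect means that the hormone carries the whole effect, so the rule can do worst in the case the hypothesis describes most fully.

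The harm is a pathway left untested and reported as no mediation, not false proof. The exact losses rest on assumed paths, a two-sided 0.05 level and a paired-difference approximation to the planned models. The n of 36 pools both age groups, whereas Aim 6 analyses them separately, so any split leaves each group smaller. A change to the plan is worth making, but not as a claim that the current rule is invalid.

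**What to change.** Remove the total-effect precondition and the criterion worded "the coefficient of sleep has decreased in absolute value from the first analysis, then a mediation effect of hormone will be concluded". For each hormone and outcome:

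- report the total effect;
- report the indirect effect, as the mean SR−HS hormone change times its slope on the SR−HS cognitive change, stating which visits form each difference;
- give a bootstrap interval that resamples participants, and base the mediation conclusion on that interval.

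State a multiplicity rule. Three hormones, two age groups and k Toolbox outcomes make 3 × 2 × k = 6k tests, and Aim 6 does not fix k. Present the older-group results as estimates with intervals only, since power there is likely to be low and the percentile bootstrap may be too liberal in so small a group. Date the change and label it as made after data collection, saying whether step-1 results were already known.

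The cost is SAP wording and some computing on data already collected. The downsides are that more results are reported and that the analysis becomes post hoc.

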Participants will perform tests included in the NIH Toolbox at baseline and week 6 of each study phase. The test battery will be performed in the morning, after an overnight fast, in conjunction with blood sampling. These computerized tests will be supplemented with the ModRey. For this test, participants are read a series of words and asked to recall them during three learning trials, after a brief delay, and after a longer delay. There is also a distractor list and a memory recognition trial. The learning and short delay trials will be administered prior to administration of the NIH Toolbox and the long delay and recognition trials will be administered afterwards. Psychometrically similar alternative forms are available and will be counterbalanced.

Structural brain imaging will be performed at Columbia University Irving Medical Center. This procedure will take place in conjunction with the whole-body scan that is currently performed in the parent study and will only be performed at baseline of phase 1. The protocol derives measures of brain atrophy/volumetry and white matter hyperintensities, but we will also examine microbleeds and infarcts for secondary analyses. Scanning will take place in a single session and include a high-resolution T1-weighted anatomical scan (MPRAGE), T2-weighted FLAIR, and gradient echo (GRE). We will also collect diffusion-weighted imaging and diffusion tensor imaging data for secondary or exploratory analyses. The MRI data will be transferred to a PACS for clinical review and via established, secure DICOM servers the data are also transferred to [name] laboratory for analysis.

---

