Sample size determination. We will enroll 66 participants and expect 50 to complete the study. This drop-out rate accounts for participant non-compliance. In our previous Sleep Study, our completion rate was 90%. We expect a larger drop-out rate in the proposed study due to the longer duration of each treatment phase, and we also anticipate dismissing some participants due to non-compliance. Each participant will undergo 2 study phases, and each response variable will be measured at least once per phase. Thus, for each response measure we will have at least  $50 \times 2$  paired observations. We have analyzed preliminary data consisting of a number of measurements from 2 overweight women from our Pilot Study. Based on preliminary data analysis we have estimated an effect size (mean paired difference) of  $0.69 \pm 0.36$  g for fat mass and an effect size (mean paired difference) of  $0.91 \pm 0.65$  g for weight gain. This translates to very large effect sizes of 1.92 (fat mass) and 1.4 (weight gain) for paired t-tests. With these effect sizes we have more than 99% power for paired t-tests.] We have estimated the EI effect size to be  $295.9 \pm 116.3$  kcal [8]. The effect size for a paired t-test (effect size divided by the standard deviation) for a paired t-test is >2, which is a very large effect size for paired t-test. This means with  $50 \times 2$  paired samples, we have >80% power for paired t-test. In [name] et al. 2011 [8], we also reported an effect size of  $20.7 \pm 6.8$  g for fat intake and an effect size of  $57.9 \pm 32.6$  g for carbohydrate intake. This translates to very large effect sizes of 3.04 and 1.78, respectively for fat and carbohydrates for paired t-test. With these effect sizes we have >80% power for paired t-test. Moreover, using the R^2 value from our linear model analysis of [name] et al. 2011, we determined that we have >80% power for proposed linear mixed model analyses (as described in statistical plan) with energy balance, fat and carbohydrate intakes. Thus, we have very good power overall, which will be useful in our primary analyses as well as in exploring sex differences. Statistical plan. Exploratory data analyses for physiological, anatomical, biomarker and intakerelated responses will be performed using R, SAS and other software. As part of the analysis, we will compute descriptive statistics for each variable. In particular, we will compute the proportion, mean, variance, standard error and the range of continuous variables and frequency and mode for discrete variables. Descriptive statistics will be computed for each specific sleep phase. In addition, correlation coefficients between the variables will be computed and scatter plots will be checked for linear relationships. The correlations and scatter plots help assess the degree of collinearity among variables, which will be useful for interpreting regression-based linear mixed model analyses discussed later. The data will be tested for normality, and if needed an appropriate transformation will be used on the raw data to make the normal approximation better. We will have a comprehensive strategy to deal with missing data. We will study missingness to decide if the data are missing at random or missing completely at random. Missing rates will also be estimated for each variable. Missing values will be imputed, as appropriate. We will fit a linear mixed model to analyze the data. Treatments (sleep duration: SR vs. HS) will be fixed effects and subjects a random effect. As we are collecting data from two phases for each subject, we will test for carryover effects by using a treatment x phase interaction in an initial version of each linear model. If the interaction term is not significant then we will rebuild the linear model without the interaction term. The other independent variables (covariates) will be sex, age, baseline BMI, and race/ethnicity. If required anywhere in the analysis plan, p-values will be adjusted for multiple comparisons. Sp. Aim 1: Hypothesis 1a. SR will lead to increased total adipose tissue mass, as assessed using MRI, relative to HS. We will perform repeated measure linear mixed model analyses separately for adipose tissue mass increase and weight gain (as the response). Sleep duration (SR vs. HS) and the covariates will be used as independent variables. Subject will be used as a random effect. Paired t-test and Wilcoxon test will be used to determine whether the SR and HS have different

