
effects on weight gain and adipose tissue mass increase. Hypothesis 1b. EE, assessed by DLW, and physical activity level, monitored daily by actigraphy, will be lower during SR relative to HS. We will perform repeated measure linear mixed model analyses separately for DLW and actigraphy-derived variables as the responses. Sleep duration (SR vs. HS) and the covariates will be used as independent variables. Subject will be used as a random effect. Paired t-test and Wilcoxon test will be used to determine whether SR and HS have different effects on DLW and actigraphy measures. Sp. Aim 2: Hypothesis 2a. EI, assessed by [3-d food records], will be greater during a period of SR relative to HS. This will be mostly due to increased fat and carbohydrate intakes. We will perform a repeated measure linear mixed model analyses separately with each EI measure (as the response) and sleep duration (SR vs. HS) and the covariates as independent variables. Subject will be used as a random effect. Paired t-test and Wilcoxon test will be used to determine whether the SR and HS have different effects on EI measures. Hypothesis 2b. Neural responses to food stimuli, assessed by fMRI after 6 wk of SR or HS, will indicate increased activity in networks associated with reward and food valuation (insula, orbitofrontal cortex) during a period of SR relative to HS. These responses will be correlated with intakes of high carbohydrate and high fat foods (hypothesis 1a) and [ghrelin]. Connectivity of the networks involved in reward valuation at rest will be stronger after SR compared to HS and synchrony of the DMN will be reduced after SR compared to HS. Sp. Aim 3: Hypothesis 3a. SR will lead to [increased glucose, insulin, triglycerides, and reduced highdensity lipoprotein cholesterol and adiponectin relative to HS.] We will perform repeated measure linear mixed model analyses separately for each of glucose, insulin, triglycerides, high-density lipoprotein cholesterol and adiponectin. Sleep duration (SR vs. HS) and the covariates will be used as independent variables. Subject will be used as a random effect. One-sided paired t-test and Wilcoxon test will also be used to determine whether the SR and HS have different effects on the cardio-metabolic risk profiles, as well as the direction of the effects. Hypothesis 3b. Increased adiposity and poor diet quality (higher fat and carbohydrates) after SR will partially explain the adverse cardio-metabolic risk profile associated with SR. We will select the cardiometabolic risk profile variables that are adversely associated with SR. Then, we will compute the difference in those variables in SR vs. HS (i.e. the value of each variable in SR minus the value of that variable in HS). Using a linear model analysis, we will test if these differences are associated with increased adiposity and poor diet quality. If, for some variables, there are multiple observed differences for each subject then a linear mixed model analysis will be used with subject as a grouping variable. A separate analysis will be performed for each such difference, with the difference as the response variables and adiposity, food quality variables and the covariates as dependent variables. *Linear Mixed Model Analyses.* We will fit a linear mixed model to analyze the data. Treatments (SR vs. HS) will be used as fixed effects and subject will be used a random effect. The other independent variables, such as demographic variables, will be covariates. Those covariates will be removed if they do not significantly contribute to the model. Aim 4: (To determine whether long-term mild SR, relative to HS, challenged acute cognitive outcomes in older and younger adults. Hypothesis 4a. Mild SR will induce cognitive decline, assessed using with the NIH Toolbox, which will be greater in older relative to younger adults.) Outcomes are measures from the NIH Toolbox. Each outcome will be analyzed in separate linear mixed model analyses, for older and young participants, as detailed in "*Linear Mixed Model Analyses*" section above. Sleep (SR vs. HS), along with phase (1 vs. 2), carryover effects, and covariates (if they are found to be significant in an initial analysis) will be used in the model. Subject will be used as a random effect. Then, we will pool the datasets to include both older and young participants. In the pooled dataset, we will use the average differences in NIH Toolbox measures (from HS to SR) as outcomes in linear model analysis. Age group (older vs. younger) will be used as main predictor variable. We will also apply covariates as independent variables, if they are found to be significant in an initial analysis. We will use unpaired t-test on the average difference in

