#### Assessment of metabolic parameters.

Fasting blood samples will be taken at baseline, wk 3, wk 4, and endpoint of each sleep phase for measuring lipid profile, glucose, insulin, adiponectin, leptin, ghrelin, and GLP-1. [92]. All samples will be analyzed in the Hormone and Metabolite Core laboratory of the NYORC (Dr. [name], Core laboratory Director) by skilled technicians. Insulin will be assayed using a radioimmunoassay (RIA; Linco Research Products Inc., St. Charles, MO; mean inter-assay CV 4.5% [93, 94]). Serum leptin will be measured using a double-antibody RIA (Linco Research; inter-assay CV 6.8% [93, 94]). Cortisol will be assay using enzyme immunoassay (DPC, Los Angeles, CA). 6-Sulfatoxymelatonin will be assayed from morning urine samples as a proxy for overnight melatonin production [95] using ELISA kit (ALPCO, Salem, NC). Blood samples will be collected in EDTA-coated chilled tubes for measuring peptide hormones. The tubes will be pre-treated with addition of aprotinin (0.6 TIU/mL of blood) and DPP-IV inhibitor (10 L/mL of blood) to prevent hormone degradation. Total ghrelin will be assessed using RIA (Linco Research; inter-assay CV 6.3% [96]). Adiponectin levels will be analyzed using RIA (Linco Research). GLP-1 will be assessed using RIA (Phoenix Pharmaceutical, Belmont, CA). An additional blood sample will be collected in silica-coated serum separating tubes to measure thyroid stimulating hormone, free T4, and sex hormones (testosterone, estrogen, progesterone, FSH, and LH).

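### Aim 6 tests mediation by hormone changes with one undefined, unsplit hormone term, so stable differences between people can produce a mediation claim

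*Combined protocol and SAP*

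**What the plan says.** In Statistical Procedures, Aim 6 applies the Baron and Kenny steps as linear mixed models with subject as the random effect: "Separately for older and young participants, and separately for each hormone measure, each outcome (from NIH toolbox) will be analyzed with mediation analysis". Step 1 regresses the cognitive outcome on sleep alone. Step 2 regresses the hormone on sleep. If both are significant, "then in the final analysis, the outcome measure will be the dependent variable. Fixed effects will be sleep and the hormone measure". The decision rule is "If the hormone measure is still found to be significant, and the coefficient of sleep has decreased in absolute value from the first analysis"; when both conditions hold, mediation is concluded.

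The hormone reading is not defined. On sampling, Assessment of metabolic parameters says "Fasting blood samples will be taken at baseline, wk 3, wk 4, and endpoint of each sleep phase", and Study Design says "Participants will perform tests included in the NIH Toolbox at baseline and week 6 of each study phase". Each phase therefore yields four fasting hormone readings and two cognitive sessions, and no pairing is given.

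Two neighbouring analyses are more specific. Hypothesis 3b states "Then, we will compute the difference in those variables in SR vs. HS". The Aim 4 model lists "Sleep (SR vs. HS), along with phase (1 vs. 2), carryover effects, and covariates". Aim 6 has no differencing, no phase term and no covariates.

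**The concern.** The hypothesis is about what changes within a person when sleep is restricted. In a model whose only random effect is subject (read here as a random intercept), a single hormone term does not isolate that. Its coefficient is a weighted average of two slopes: the within-person slope, and the slope across people, who differ in sex, BMI and much else that may relate to both hormone level and test score. The crossover protects the sleep contrast from such differences. It does not protect the hormone coefficient.

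The decision rule passes this mixture on. Once SR has shifted both hormone and cognition, any non-zero blended slope of the right sign reduces the sleep coefficient, and the rule accepts any reduction. No interval or test is attached to the indirect effect. The rule is run for three hormones, every Toolbox measure and two age groups, so a reported mediator might show only who has high leptin or insulin.

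**Working it through.** **Inputs from the documents.** No power figure or error rate is stated for Aim 6, so there is none to reproduce. Group sizes must be inferred. For the parent cohort, "We will enroll 66 participants and expect 50 to complete the study". Subject Population Justification gives a target accrual of 79, and the Subjects section reports 36 completers.

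- Older participants: 79 − 66 = 13; completers 13 × 50/66 ≈ 10.
- Young completers: 36 − 10 = 26.

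The assumed range is therefore n = 10 to 26 per age group.

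**Assumptions.** Hormone intraclass correlation (ICC) 0.85 and cognition ICC 0.6, with total variances set to 1. Sleep effects are expressed as dz (mean paired difference over its SD) on both variables. SR is taken to raise the hormone and lower the score, so a negative between-person correlation rho is the claim-producing sign; for a hormone that SR lowers, the sign reverses. The true within-person slope is 0, so every mediation claim is false. Two-sided alpha is 0.05.

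**Mechanism by hand** (one reading per phase; approximate, because it ignores the small drop in residual variance from adding the hormone).

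- Variance of a person's mean hormone: 0.85 + 0.15/2 = 0.925. Variance of the paired difference: 2 × 0.15 = 0.30.
- Between-person slope: rho × √(0.85 × 0.6)/0.925 = 0.772 × rho, which is −0.232 at rho −0.3 and −0.386 at rho −0.5.
- Information per person, between: 2 × 0.925/(0.4 + 2 × 0.6) = 1.156. Within: (0.30/2)/0.4 = 0.375.
- Weight on the between-person slope: 1.156/(1.156 + 0.375) = 0.755.
- Blended coefficient: 0.755 × (−0.232) = −0.175, or 0.755 × (−0.386) = −0.291. Simulated means with hormone ICC 0.8-0.9 and cognition ICC 0.5-0.8 were 0.16-0.20 and 0.27-0.34 in size, which agrees.
- At dz 0.7 the hormone shift is 0.7 × √0.30 = 0.383, and the step 1 sleep coefficient is −0.7 × √0.80 = −0.626.
- Step 3 sleep coefficient: −0.626 + 0.175 × 0.383 = −0.559 (about 11% smaller), or −0.626 + 0.291 × 0.383 = −0.515 (about 18% smaller). Neither reduction reflects mediation.

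**Simulated false-claim rates under the rule as written** (hormone entered as a level, 6,000 trials per scenario, random-intercept REML):

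| Scenario | rho −0.3 | rho −0.5 |
|---|---|---|
| n = 10-26, dz 0.7 | 3-18% | 5-42% |
| n = 10-26, dz 0.5 | 1-9% | 2-24% |
| n = 10-26, dz 0.3 | under 2% | at most 5% |
| n = 10-26, trials passing steps 1 and 2 | 10-20% | 20-53% |
| n = 36-50, dz 0.7 | 25-34% | 60-76% |
| n = 13-26, dz 0.7, hormone ICC 0.6-0.95, cognition ICC 0.4-0.8 | 3-22% | 6-54% |

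At n = 10-26 the rate is at most about 2% at rho 0 and at most 0.3% at rho +0.3.

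**Comparators.** The within-person difference regression, with the same two significance steps, gives about 3% or less at every n examined. If the hormone is entered as change from the phase baseline, the rule as written gives 0.3-1.8% at n = 10-26 and dz 0.7.

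**The case against.** The strongest reply is that several conditions must hold together: a level is entered, SR has a sizeable effect on both variables, and the between-person correlation has the claim-producing sign. The documents supply none of these values, and in part of the plausible range the error is at or below 5%. The wording of Hypothesis 6a also suggests change scores, which would largely remove the problem. Both points are right. They make the error conditional, but the text does not commit to change scores.

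The group sizes are also soft. The figure of 26 subtracts a projected count from an actual one. Study Design gives the cognitive tests only to parent-cohort participants enrolled during the supplement award, so the young group may be smaller. That lowers the overall rate, mainly because fewer trials pass the first two steps.

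Multiplicity adjustment is promised only if required, with no method named. With alpha of 0.05/3 at every step (an assumption), the dz 0.7 rates fall to 0.1-6.9% and 0.4-24.6%: smaller, not gone.

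It can also be said that comparing the two sleep coefficients implicitly estimates an indirect effect. It does, but with the same contaminated slope and without an interval.

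The general covariate text in Statistical Procedures does not rescue the analysis, because Aim 6 lists its own fixed effects and restricts step 1 to sleep alone.

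Finally, the remedy does not remove time-varying confounding within people. With a within-person residual correlation of −0.3, rho 0 and no mediation, the within-person test gives more false claims than the plan: 7-28% against 4-14% at n = 13-26, and 41-56% against 20-26% at n = 36-50. If rho is also −0.3, the order reverses at n = 13-26: 7-28% against 12-47%. This objection stands, and it is why the aim should be called exploratory.

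**Conclusion.** The concern holds. As written, Aim 6 can declare mediation by hormone changes from stable differences between people, because the hormone term is neither defined nor split. The rates illustrate direction and size and are not estimates for this trial. They rest on assumed ICCs, correlations, sleep effects and group sizes, and on the level reading. Within that level reading, larger samples make the error more frequent. The problem is confined to a supplementary aim and leaves the energy-balance aims untouched, but it should be corrected before any mediation result is reported.

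**What to change.** 1. State which hormone and Toolbox readings enter Aim 6, and whether as endpoint values or as change from that phase's baseline.
2. Regress the SR-minus-HS cognition difference on the SR-minus-HS hormone difference with sequence as a covariate. Equivalently in purpose, fit the mixed model with person mean and within-person deviation as separate hormone terms plus phase. Interpret only the within-person coefficient.
3. Report the indirect effect (mean hormone difference × within-person slope) with a 95% interval, and conclude from that interval rather than from a reduced sleep coefficient. A Monte Carlo interval with t draws gave at most 4.6% false claims at n = 10-36 and dz 0.7; a percentile bootstrap gave 5-7%.
4. Label Aim 6 exploratory and say that the hormone is not randomised.

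The cost is plan wording and modest programming on data already collected. Power is low: a within-person correlation of −0.3 would be detected in only about 10-30% of trials at n = 13-26 and dz 0.7. Because the study is now open for analysis only and a cognitive-function paper is already in press, the choice of readings should be dated and described as made after data collection.
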